4.2 Inclusion Criteria

1. Healthy women of 18 years of age or older and non-childbearing potential (i.e., prior hysterectomy or bilateral tubal ligation; last menstrual cycle more than 12 months prior to

study enrollment or serum FSH >40 IU/L if woman has not had a bilateral tubal ligation or hysterectomy).

2. Clinical symptoms of overactive bladder for 6 months or longer including at least one of the following:
 - a. Frequent micturition ≥ 8 times per 24 hrs
 - b. Symptoms of urinary urgency (the complaint of sudden compelling desire to pass urine, which is difficult to defer) or nocturia (the complaint of *waking* at night two or more times to void)
 - c. Urge urinary incontinence five or more incontinence episodes per week based on 7-day voiding diary. Urge urinary incontinence is defined as: the complaint of involuntary leakage accompanied by or immediately preceded by urgency.
3. Detrusor overactivity with ≥ 1 uncontrolled phasic contraction(s) of the detrusor of at least 5 cm/ H₂O pressure documented on cystometry at Screening Visit 1A (i.e., prior to study drug administration at Visit 2).
4. Bladder scan or direct catheter drainage demonstrating a residual volume of ≤ 200 ml
5. Non-response or response but poor tolerance to a previous treatment for symptoms of overactive bladder/urinary incontinence (e.g., anti-muscarinic/ anticholinergic agents, or Botox) or do not wish to continue these treatments.
6. Able to understand study requirements (i.e., literate in English), give written informed consent, and comply with all study procedures and requirements.

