Efficacy evaluations will include the number of micturitions per day, volume per micturition, urgency episodes and incontinence (or accident) episodes from voiding diary, and pad weight. Efficacy evaluations will also include the following cystometric evaluations performed by the site and/or the overreader at week 4 and 24: 1) Detrusor overactivity ≥ 5 cm H₂O (yes/no- INCLUSIONCRITERIA); 2) Volume at first desire to void; 3) Detrusor pressure at beginning of voiding (prior to onset of first contraction, either volitional or involuntary); 4) Volume at first involuntary contraction; if detrusor overactivity (DO) present-Not applicable if no DO present; 5) Maximum detrusor pressure at FIRST contraction.

PVR on bladder scan, and general and bladder specific quality of life assessments measured by participant evaluation using Kings Health Care Questionnaire (KHQ) and participant evaluation of response to treatment will also be evaluated.

Statistical methods:

Both the safety data and data to assess efficacy will be summarized using summary descriptive statistics by treatment group (combined placebo vs. 2 active treatment groups and combined placebo vs. combined treatment groups) and the total study population.

Linear mixed effect models will be used to estimate difference of changes from baseline between placebo and active treatment and to test whether there is dose-response for different outcomes. Generalized estimating equation (GEE) model will be used to estimate effects for the binary endpoints.

TABLE OF CONTENTS

STATISTICAL ANALYSIS PLAN	1
SIGNATURE PAGE	2
REVISIONS HISTORY LOG	2
SYNOPSIS.....	3
TABLE OF CONTENTS.....	6
LIST OF TABLES	8
1. LIST OF ABBREVIATIONS.....	9
2. INTRODUCTION	11
3. STUDY OBJECTIVES	12
3.1. Primary Objectives	12
3.2. Secondary Objectives	12
4. STUDY DESIGN	13
4.1. General Study Design and Plan	13
4.2. Study Population.....	13
4.2.1. Selection of Study Population.....	13
4.2.2. Subject Withdraw and Replacement.....	14
4.3. Randomization and Blinding.....	14
4.4. Study Assessments.....	14
4.4.1. Safety Assessment	19
4.4.2. Outcome Assessments	19
5. SAMPLE SIZE DETERMINATION	20
6. ANALYSIS POPULATIONS	21
7. GENERAL STATISTICAL CONSIDERATIONS.....	21
7.1. Interim Analyses and Data Monitoring	21
7.2. Multi-Center Studies.....	21
7.3. Multiple Comparisons / Multiplicity	21
7.4. Examination of Subgroups	21
7.5. Handling of Dropouts or Missing Data.....	21
7.6. Outlier Handling	21

7.7.	Adjustments for Covariates	21

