3.2. Secondary Objectives

The secondary objectives of this study are to evaluate the following safety parameters:

- Clinical laboratory tests - changes from baseline
- Electrocardiogram - changes from baseline
- Vital signs - changes from baseline

In addition, efficacy parameters will be evaluated as change from baseline compared to placebo. Comparisons will be made between combined placebo (N = 6) vs. 16,000 µg (N = 6) and 24,000 µg (N = 6) active *h*Maxi-K group separately, and also between combined placebo and combined active group (N = 12), as well as between treatment comparisons for a dose response analysis. Efficacy evaluations will include the number of micturitions per day, volume per micturition, urgency episodes (1 or greater) and incontinence episodes (accidents) from voiding diary, and pad weight. Efficacy evaluations will also include the following cystometric evaluations performed by the overreader at week 4 and 24: 1) Detrusor overactivity ≥ 5 cm H²O (yes/no- INCLUSION CRITERIA); 2) Volume at first desire to void; 3) Detrusor pressure at beginning of voiding (prior to onset of first contraction, either volitional or involuntary); 4) Volume at first involuntary contraction; if detrusor overactivity (DO) present-Not applicable if no DO present; 5) Maximum detrusor pressure at FIRST contraction.

PVR on bladder scan, and general and bladder specific quality of life assessments measured by participant evaluation using Kings Health Care Questionnaire (KHQ) and participant evaluation of response to treatment will also be evaluated.

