4.4.2. Outcome Assessments

OAB / DO Objective Assessment: Cystometry

Clinical assessment of the efficacy hypothesis that *hMaxi-K* will reduce detrusor overactivity. Detrusor overactivity will be assessed with two standardized, sitting position, saline cystometries followed by pressure flow studies (see Protocol Appendix D). Every attempt should be made to perform the studies at the same time of day and in the same way for each participant. Studies are to be completed at V1A (screening), V5 (4 weeks post dosing with study drug) and V8 (or Final Visit). An over-reader will interpret the results as well as the investigator, however, the over reader's interpretation will take priority for the analysis.

Clinical Evaluation of OAB / DO

Voiding Diary

Clinical signs and symptoms of OAB / DO will be determined by a daily voiding diary. The participants must complete the diaries for the 7 days prior to the Baseline Visit (Visit 2), and for 7 days prior to Visits 3 to 8. The participants will also complete the diaries prior to Visit 1A to test for compliance and evaluate for some inclusion criteria. The site will contact the participant 7 to 8 days prior to the scheduled visit (Visits 2 to 8) to remind the participant to complete the diary. The daily voiding diary will collect standard bladder function and frequency parameters including frequency of micturitions, volume voided and urgency (1 or greater on scale) and incontinence (accidents) episodes. The urgency questionnaire is a 4 point scale with 1 to 4 indicating the presence of urgency. See Protocol Appendix F.

Pad Test

Each participant will record their use of any pads/panty liners (eg, Poise[®] pads or Depends[®], etc.) in their diary. The participant will bring in pads/diapers worn prior to Visit 1A and for the three days prior to Visit 2 (as well as a new pad/diaper to use as a baseline) and for the 3 days prior to all subsequent visits (Visits 3 to V8). Used pads/diapers will be stored in a plastic bag provided by the site and weighed upon receipt and compared to the clean pad. All pads/diapers used by the participants for the 7 days prior to each visit, will be counted by the participants and entered in the voiding diary by them.

King Health Questionnaire and Assessment of Disease State/Treatment

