9. EFFICACY ANALYSES

9.1. Primary Efficacy Analyses

The per participant listing for voiding diary (Dispense Daily Voiding Diary/Urgency Questionnaire) will be presented in Listing 16.2.6.1. The cystometry overread parameters will be presented in Listings 16.2.6.2.1 and 16.2.6.2.2, and in Listings 16.2.6.2.3 through 16.2.6.2.5 for site investigator read. The bladder scan per subject will be detailed in Listing 16.2.6.3 and the pad test in Listing 16.2.6.4. The QoL survey will be presented in two listings with King's Health Questionnaire (KHQ) in Listing 16.2.6.5.1 and SF-12 in Listing 16.2.6.5.2. Per participant assessment of disease and response to treatment will be detailed in Listing 16.2.6.6. Also, participant response to International Consultation on Incontinence Questionnaire (ICIQ) Short Form will be presented in Listing 16.2.6.7. The primary efficacy result, the reduction of the number of voids per day compared to placebo using voiding diary data, will be presented in Table 14.2.1.1. Assuming the number of voids follows a normal distribution, we will test whether there is significantly more reduction in the treatment group at each time point, where there are difference between treatment groups for the pooled *h*Max-K group vs. the placebo group using linear mixed effect model adjusting for the clustering effect by each individual with treatment, time and interaction of time and treatment. We will also present the summary statistics of voiding at each visit and change from baseline at each postdose time point. Difference in change and corresponding 95% confidence interval from baseline for each treatment group vs. placebo and 24,000 µg vs. 16,000 µg will also be presented in Table 14.2.1.1.

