P_{abd} (cm H ₂ O)	Maximum abdominal pressure during any contraction	MAXIMUM abdominal pressure during ANY contraction. This will assess the abdominal straining component to voiding ^{c,d}
a To be analyzed b This is done by overreader, but not the sites c Listing only; not analyzed d Done by site only e Detrusor pressure at first involuntary contraction is called “ Detrusor Pressure ” for sites on eCRF. f Maximum detrusor pressure at ANY contraction is called “ Maximum Detrusor Pressure ” for sites on eCRF.		

The Cystometry overread parameters will be used for objective evaluation analyses. Binary outcomes will be estimated using generalized estimating equation (GEE) model with binary distribution and a logistic link clustered by participant. The parameters that can be treated as continuous variables will be analyzed similarly to the primary efficacy endpoint using linear mixed effect model adjusting for clustering effect by participants.

The mapping of the cystometry parameters that will be analyzed and the corresponding tables that will be used to present the results are shown in [Table 3](#).

Table 3: Cystometry Parameter Analysis Endpoints and Tables that will present the Analysis Results

1) Detrusor overactivity ≥ 5 cm H ₂ O (yes/no- INCLUSION CRITERIA)	Table 14.2.4.1: Cystometry Overread: Change in the Presence and Absence of Detrusor Overactivity (DO)
2) Volume at first desire to void	Table 14.2.4.2: Cystometry Overread: Change of Volume at First Desire to Void (mL)
3) Detrusor pressure at beginning of voiding (prior to onset of first contraction (either volitional or involuntary))	Table 14.2.4.3: Cystometry Overread: Change from Baseline for Detrusor Pressure Prior To Onset of First Contraction (Either Volitional Or Involuntary) (cm H ₂ O)
4) Volume at first involuntary contraction; if detrusor overactivity (DO) present-Not applicable if no DO present	Table 14.2.4.4: Cystometry Overread: Change from Baseline for Volume of First Involuntary Detrusor Contraction (mL) in Presence of Detrusor Overactivity
5) Maximum detrusor pressure at FIRST contraction	Table 14.2.4.5: Cystometry Overread: Change of Maximum Detrusor Pressure at FIRST Contraction (Voluntary or Involuntary) (cm H ₂ O)

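### With 6 participants per group, the planned GEE for detrusor overactivity (DO) yes/no may have no estimable odds ratio, and the SAP gives no sparse-cell rule

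*SAP*

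**What the plan says.** SAP 9.2 assigns DO yes/no, from the cystometry overread, to a logistic GEE: "Binary outcomes will be estimated using generalized estimating equation (GEE) model with binary distribution and a logistic link clustered by participant". The SAP synopsis repeats this: "Generalized estimating equation (GEE) model will be used to estimate effects for the binary endpoints". The result goes into Table 14.2.4.1.

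SAP 3.2 sets the comparisons: 6 pooled placebo against 6 at 16,000 µg and 6 at 24,000 µg separately, pooled placebo against 12 pooled active, and a dose-response analysis. Cystometry is done at screening Visit 1A, Week 4 and Week 24 (SAP 4.4.2). Protocol 4.2 requires DO for entry, "documented on cystometry at Screening Visit 1A".

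For this GEE the SAP names no model terms, working correlation, variance estimator, test, small-sample correction or rule for an empty cell. The terms in SAP 9.1, "with treatment, time and interaction of time and treatment", belong to the linear mixed model for voids. SAP 9.2 carries that approach over to continuous cystometry parameters, not to the binary one. SAP 9.3 adds only that other models could be explored.

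**The concern.** A logistic model has no finite odds ratio when a group it estimates separately is all-yes or all-no. With six women per group, all with DO at entry, such a cell is easy to reach: every woman in one arm need only keep her DO. The same happens if DO disappears in a whole arm.

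The fit may not stop with an error. It can report convergence, a very large coefficient and a moderate robust standard error, and hence an extreme p-value. SAP 13.2 would print that as below 0.001. Reduction of DO is the efficacy hypothesis that both documents state for cystometry (Protocol 6.2, SAP 4.4.2), and change in DO is a listed secondary outcome. A spurious p-value here could be read as an early signal of activity or dose response.

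**Working it through.** **Plan's own figure.** There is none for DO. The only power statement (0.80251, in SAP 5) concerns voids per day with groups of 9 and 10; it does not bear on this point.

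**Inputs.** From the documents: 6, 6 and 6 per group, 12 pooled active, two post-dose visits. Assumed: a common post-dose DO rate p, shown from 0.5 to 0.9, and two-sided 5% tests. The 6/6 versus 5/6 split is illustrative.

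**Step 1: chance of a degenerate cell.** For one cell of six, q = p^6 + (1−p)^6. At p = 0.8, q = 0.2621 + 0.0001 = 0.262. For at least one of six independent cells (3 arms × 2 visits), the chance is 1 − (1−q)^6 = 1 − 0.738^6 = 0.84. At p = 0.5 and 0.6 it is 17% and 27%. For three arms at one visit, 1 − (1−q)^3 gives 31%, 60% and 90% at p = 0.7, 0.8 and 0.9. Positive correlation between a woman's two visits moves the six-cell figure down towards these. The formula is symmetric, so rates of 0.3, 0.2 and 0.1 give the same results.

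**Step 2: what the fit returns for 6/6 versus 5/6 at one visit.** Calculated with Python statsmodels, which reports convergence:
- The log odds ratio stops at about −21. This is only where iteration ended.
- The robust SE is 1.10 = √[1/(6 × 5/6 × 1/6)] = √1.2, all from the 5/6 arm. Then z ≈ −20.96/1.095 = −19.1 and p ≈ 1e-81.
- Bias-reduced robust SE 1.31: p<1e-56.
- Model-based SE 32,440: p>0.999.
- Robust score test: p = 0.30.
- Fisher: the single 'no' falls in either arm with probability 1/2, so two-sided p = 1.00.
- Adding 0.5 to each cell (Firth-type): log OR = ln(5.5/1.5) − ln(6.5/0.5) = −1.27, SE 1.73, p = 0.47.

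Pooled active, 6/6 versus 11/12, gives robust p ≈ 1e-83 and Fisher p = 1.00. Without a degenerate cell the model behaves: 5/6 versus 4/6 gives p = 0.51.

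**Step 3: false positives with no true effect.** In the one-visit, 6 versus 6 comparison the robust Wald test rejects whenever exactly one arm is degenerate, which has probability 2q(1−q). At p = 0.8 this is 2 × 0.262 × 0.738 = 0.387; full enumeration gives 0.388. The additive column is simulated (3 arms of 6, two post-dose visits, robust Wald, one dose versus placebo); its ranges span simulation runs.

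| Assumed DO rate | q | Any of 6 cells | Robust Wald, one visit, 6 v 6 | Same, 12 v 6 | Additive treatment + time | Fisher, 6 v 6 |
|---|---|---|---|---|---|---|
| 0.7 | 0.118 | 53% | 21.5% | 14.9% | 5–7% | 0.3% |
| 0.8 | 0.262 | 84% | 38.8% | 30.4% | 8–15% | 0.09% |
| 0.9 | 0.531 | 99% | 49.8% | 51.4% | about 30% | 0.01% |

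At p = 0.5 the one-visit robust Wald rates are 7.9% (6 v 6) and 5.4% (12 v 6).

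**The case against.** The strongest reply is that the severe error rates belong to a model the SAP does not state. They need arm-by-visit cells and a robust Wald test. An additive model gives much less inflation at rates of 0.7 and 0.8, and model-based standard errors give p near 1 for 6/6 versus 5/6. This stands. A reader might infer that the plan as written will turn 6/6 versus 5/6 into a significant result, or that six per arm alone breaks the GEE. The documents support neither: the outcome depends on unstated choices, and a degenerate cell is what breaks the model.

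A reader might also assume that DO will stay common after dosing. The documents give no post-dose rate. Protocol 1.4.2 reports a reduction above 80% in detrusor contractions in one earlier dose group; that is a different measure, but it lends the assumption no support. Nor does any section put the all-yes baseline visit into the GEE, although the title of Table 14.2.4.1 speaks of change.

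A log odds ratio near −21 beside counts of 6/6 and 5/6 should catch an analyst's eye, and SAP 13.1 names SAS or Stata, which may stop at a different value. But noticing the problem does not say what to report. SAP 9.3 leaves the replacement to be chosen after the data are seen.

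SAP 7.3 calls the efficacy p-values nominal and exploratory. That deals with multiplicity and limits the consequence; it does not make an invalid p-value usable.

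**Conclusion.** The concern holds in a limited form. When a modelled arm or arm-by-visit cell is all-yes or all-no, no choice of variance estimator or test makes the GEE odds ratio estimable. The SAP has no rule for that case. The same data can then give p<0.001, p = 0.30 or p near 1, depending on a choice it leaves open.

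The probabilities rest on assumed DO rates, equal across arms, and for the six-cell figure on independent cells. At rates near 0.5 the problem is modest. Baseline is all-yes by eligibility, unless the overread disagrees with the site read.

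This should be fixed, but it is not critical. DO yes/no is one of five analysed cystometry parameters, the primary objective is safety, and no stopping or escalation rule uses DO. A reader might infer that the trial's main conclusions are at risk; the documents do not support that.

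**What to change.** In SAP 9.2, make the DO yes/no analysis exact, separately at Week 4 and Week 24:
- Fisher's exact test, with an exact confidence interval for the risk difference (name the method), for each dose and for pooled active against pooled placebo.
- An exact Cochran–Armitage trend test over placebo, 16,000 µg and 24,000 µg for dose response. SAP 9.2 already uses Cochran–Armitage for response to treatment.

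If a joint model across visits is kept, use a Firth-type penalised logistic model on post-dose visits only. State its terms, how repeated visits are handled, and the variance estimator. Align the synopsis sentence. SAP 2 requires the plan to be final before the blind is broken, so the change belongs before then.

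The cost is SAP wording and simpler code. The exact route gives up a joint model across visits and has little power. Against 6/6, Fisher reaches p<0.05 only at 1/6 or fewer: 2 × 6/792 = 0.015 at 1/6, but 2 × 15/495 = 0.061 at 2/6. True rates of 0.9 and 0.3 would be detected about 26% of the time. The interval should therefore carry the interpretation.

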10.3 Efficacy

The sample size has been estimated assuming a standard deviation of 2.5 and a two sample t-test to have 80% power.

The protocol is designed to observe a 30% reduction in the number of voids compared to placebo following gene transfer using the following calculations with NCSS/PASS program (NCSS, Kaysville, Utah, 84037-3233).

Table 10;. Powering									
Power	N1	N2	Ratio	Alph	Beta	Mean	Mean2	S1	S2
0.80251	9	10	1.111	0.050	0.19749	10.0	6.6	2.5	2.5

The mean number of micturations per 24 hours will be evaluated at all visits and changes compared to baseline and placebo.

The other secondary outcome measures will be the change in the mean number of urge incontinence episodes per 24 hours; urgency episodes per 24 hours; mean volume voided per micturition, diminished urgency perception; change in weight of 72 hour pad test; and change in

detrusor overactivity (DO) including peak amplitude, volume at which DO appears and presence or absence of DO. The participants' perception of their bladder condition and response to treatment will be assessed at baseline (Week 0) and after 1, 2, 4, 8, 12, and 24 weeks. Improvement will be defined as a decrease of 1 point or more from baseline. Quality of Life (QoL) will be evaluated using the Kings Health Questionnaire (see Appendix B for algorithm). Change in maximum bladder capacity (difference of pre-treatment to post-treatment volume) as determined by cystometry of *hMaxi-K* versus pool of placebo participants from each treatment level.

Participants will be assessed for changes from baseline in urinary symptoms following administration of *hMaxi-K* using the questions of the ICIQ-SF form and the urgency rating scale. Participants will also be pooled across treatment groups (all active vs. all placebo).

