APPENDIX D. Cystometry Procedure Guidance

The importance of performing well-controlled cystometries cannot be over-emphasized. The methodology advocated by the International Continence Society in *Neurourology and Urodynamics* 21:261-274, 2002 should be followed.

Minimally, patients should be positioned in the sitting position. Using sterile aseptic techniques, a 7 or 8 Fr double-lumen transurethral catheter will be inserted into the urethra and a 9 Fr balloon catheter will be placed in the rectum to measure abdominal pressure. Room-temperature saline will be used at a filling rate of 50 ml/min. Either fluid filled catheters connected to pressure transducers or solid-state catheters should be used to help minimize artifact. The same system must be used for pre and post transfer studies on each patient. Participants should be instructed to neither void nor to try to inhibit micturition, but to simply report their sensations to the examiner. Participants should be instructed to indicate first desire to void, strong urge to void, and/or when they can no longer tolerate infusion (i.e. no longer delay micturition). Bladder filling should be discontinued as soon as the participant experiences a strong desire to void, uncomfortable fullness or pain.

Digitized recordings should be captured and stored for each participant. Waveforms from filling cystometries and pressure flow studies should be interpreted by a trained professional for each parameter noted in the following Table A. A cystometry overreader as well as the investigator will be required to interpret the results. The central overreader's interpretation will take priority. Printed waveforms should be kept with the patient's source records, with items such as artifacts and peak pressure measurements clearly identified. Digitized pressure recordings will be analyzed for the following parameters:

Table A: Cystometry Parameters and Definitions

Parameter	Description	Definition
DO; Yes/No	Detrusor overactivity ≥ 5 cm H ₂ O	Any involuntary contraction that has a pressure ≥ 5 cm H ₂ O (INCLUSION CRITERIA)
V _{First des} (mL)	Volume at first desire to void	The volume attained during filling cystometry that would lead the patient to pass urine at the next convenient moment but voiding can be delayed if necessary (ICS definition).

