7.5. Handling of Dropouts or Missing Data

Handling of missing concentration data will be detailed in PK analysis plan and/or report. Missing data for adverse events, laboratory test will not be imputed. Last observation carried forward (LOCF) will be used to impute efficacy endpoints.

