9.2. Secondary Efficacy Analyses

Change in the mean number of urge incontinence episodes per 24 hours, change in mean number of urgency episodes, and change in the mean volume voided per micturition will be analyzed similarly as the primary efficacy endpoint and presented in Tables 14.2.1.2 through 14.2.1.4. Change in weight of 72 hour pad test and change in residual volume from bladder scan will also be analyzed and presented similarly in Tables 14.2.2 and 14.2.3 respectively.

Definitions of cystometric parameters are displayed in Table 2. The site readings and many of the overreader readings will be presented by subject in listings. Five of the overreader parameters will be analyzed, variables 1, 2, 3, 4 and 12, are displayed in [Table 2](#). The corresponding output table numbers and titles for these 5 variables are displayed in [Table 3](#). We may do additional exploratory analyses for additional cytometry parameters, if necessary.

Table 2: Cystometric Parameters and Definitions

Parameter	Description	Definition
DO; Yes/No	Detrusor overactivity ≥ 5 cm H ₂ O	Any involuntary contraction that has a pressure $> / = 5$ cm H ₂ O (INCLUSION CRITERIA) ^a
V _{First des} (mL)	Volume at first desire to void	The volume attained during filling cystometry that would lead the patient to pass urine at the next convenient moment but voiding can be delayed if necessary (ICS definition). ^a
P _{det. open} (cm H ₂ O)	Detrusor pressure at beginning of voiding (prior to onset of first contraction (either volitional or involuntary)	Detrusor pressure at onset of the first detrusor contraction (either volitional or involuntary). ^a
V _{1st} (mL)	Volume at first involuntary contraction; if detrusor overactivity (DO) present. Not applicable if no DO present.	Volume infused at the point of maximum detrusor pressure during the 1 st contraction. ^{a,b}
Det _{freq}	Total number of detrusor contractions during procedure (voluntary AND involuntary)	Total number of detrusor contractions including voluntary AND involuntary ^c
Leak (Yes/no)	Was there a leak with overactivity	Involuntary detrusor contractions resulting in leak (NOT counting voluntary voids) ^c
DO _{Leak freq}	Number of involuntary detrusor contractions resulting in leak (if DO present)	Number of involuntary detrusor contractions resulting in leak (if DO present) ^{b,c}
V _{leak} (mL)	If yes, Volume of each leak	Volume of each leak for each episode of leak ^{c,d}

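### SAP Table 14.2.4.4 compares the volume at first involuntary contraction only among women who still have detrusor overactivity after treatment, and SAP 7.5 does not exempt the resulting blanks from LOCF

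*SAP*

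**What the plan says.** SAP Table 2 describes V1st as "Volume at first involuntary contraction; if detrusor overactivity (DO) present. Not applicable if no DO present". Only the overreader reads it, and a footnote marks it for analysis. Table 3, row 4, maps it to output Table 14.2.4.4, titled "Change from Baseline for Volume of First Involuntary Detrusor Contraction (mL) in Presence of Detrusor Overactivity". Continuous cystometry variables are to be "analyzed similarly to the primary efficacy endpoint using linear mixed effect model adjusting for clustering effect by participants". By SAP 9.1 that means change from baseline, with each dose and the pooled active group compared with placebo. SAP 3.2 gives the group sizes: 6 placebo, 6 per dose, 12 pooled active.

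SAP 7.5 states: "Last observation carried forward (LOCF) will be used to impute efficacy endpoints". It makes no exception for a value that is not applicable, and it does not say whether baseline may be carried.

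Protocol 4.2 requires DO "documented on cystometry at Screening Visit 1A". Cystometry is repeated at weeks 4 and 24. SAP 4.4.2 gives the efficacy hypothesis as a reduction in DO. DO yes/no has its own analysis by GEE (Table 3, row 1; Table 14.2.4.1). Protocol 10.3 names both "volume at which DO appears and presence or absence of DO" as outcomes. On the end of a filling study, Protocol Appendix D says: "Bladder filling should be discontinued as soon as the participant experiences a strong desire to void, uncomfortable fullness or pain".

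**The concern.** A woman enters with DO, so she should have a baseline V1st. If she has no involuntary contraction at week 4 or 24, her threshold was not reached at the volume infused. That is information about V1st: it lies above that volume. The plan discards it. Who is compared then depends on what happened after randomisation, on the very outcome the drug is expected to change.

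Losing DO is plausible on the sponsor's own data. Protocol 1.2 reports near-complete removal of DO in treated rats at the two higher doses. Protocol 1.4.2 reports a fall of more than 80% in detrusor contractions against baseline at week 24 at 5000 µg in the earlier bladder trial. With six women per dose, two or three such cases leave an estimate based on three or four.

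The SAP also leaves open whether these blanks are dropped or filled. If filled, a woman without DO gets a value from a visit at which DO was present: week 4, or baseline if that may be carried.

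**Working it through.** **Figures in the plan.** None is given for V1st. The only design calculation (SAP 5, number of voids, power 0.80251) plays no part here.

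**Inputs from the documents.** Groups of 6, 6 and 6; DO required at entry; V1st not applicable without DO; LOCF for efficacy endpoints. Means, SDs, bladder capacity and the share losing DO are not given and are assumed below.

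**Step 1: arithmetic on six treated women.** Assume a gain of 50 mL where DO persists, and assign 150 mL to a woman whose DO has gone. With k women losing DO:

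- all women: (150k + 50(6 − k)) / 6
- dropped: 50, on n = 6 − k
- baseline carried (change = 0): 50(6 − k) / 6

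| k | All women | Dropped (n) | Baseline carried |
|---|---|---|---|
| 0 | 50 | 50 (6) | 50 |
| 2 | 83 | 50 (4) | 33 |
| 4 | 117 | 50 (2) | 17 |

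Dropping leaves the estimate flat while n falls. Carrying baseline lowers it as more women respond. In the all-or-none extreme (3 lose DO, 3 unchanged), Table 14.2.4.4 would show a mean change of 0 mL either way, on n = 3 or n = 6, while Table 14.2.4.1 would show 3/6 = 50% without DO.

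**Step 2: simulation, threshold against capacity.** Let B be baseline V1st, F = B + shift + noise, and C the capacity; DO is absent at follow-up if F ≥ C. Assumed: SD of B 60 mL, SD of the noise 50 mL, entry only if B < C. Each effect is the active mean minus that of a zero-shift placebo arm:

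- capped: mean of min(F, C) − B, all women
- dropped: mean of F − B where F < C
- baseline carried: mean of F − B, set to 0 where F ≥ C

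| Mean B / C (mL) | True shift | Active without DO | Capped | Dropped | Baseline carried |
|---|---|---|---|---|---|
| 180 / 300 | 50 | 17% | 45 | 44 | 37 |
| 180 / 300 | 100 | 39% | 81 | 83 | 52 |
| 180 / 300 | 200 | 85% | 118 | 153 | 26 |
| 180 / 400 | 50 | 2% | 50 | 49 | 48 |
| 180 / 400 | 100 | 6% | 98 | 96 | 90 |
| 180 / 400 | 200 | 40% | 178 | 179 | 108 |
| 120 / 300 | 50 | 5% | 49 | 47 | 45 |
| 120 / 300 | 100 | 16% | 94 | 92 | 77 |
| 120 / 300 | 200 | 63% | 156 | 166 | 62 |

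Dropping keeps between 153/200 = 77% and 49/50 = 98% of the true shift. Carrying baseline keeps between 26/200 = 13% and 48/50 = 96%.

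**Step 3: a second set of assumptions.** Threshold 170 ± 70 mL, end of filling 260 ± 60 mL, SD of the change 50 mL. For true shifts of 80 and 120 mL, just over a third and about 55% of active women lose DO. Dropped: 71 and 106 mL (89% and 88% of the shift). Capped: 65 and 87 mL. Baseline carried: 46 and 49 mL.

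**Limits.** These are single-visit differences in means, not the planned mixed model. Carrying the week 4 value to week 24 was not simulated.

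**The case against.** The strongest defence is that the two outputs form a pair: Table 14.2.4.1 asks whether DO stopped, and Table 14.2.4.4 asks at what volume it starts if it did not. The conditioning is printed in the title, SAP 13.2 makes n the count of non-missing values, and overread values are listed by subject. This holds for a descriptive table. It does not hold for a between-group test, because the SAP neither links the two tables nor warns that the second excludes women whose DO resolved.

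It can also be said that LOCF is for missing data, that 'not applicable' is a recorded state, and that filling it would contradict the table title. That is a fair reading, but SAP 7.5 does not state it.

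A reader might infer that this endpoint would show no effect because the drug worked, with the best responders counted as unchanged. The documents do not support that as a general statement. If blanks are dropped, the mean shift is largely kept, and at large shifts it exceeds the capped value; zero arises only in the all-or-none case. 'Unchanged' is literal only if baseline is carried, which the SAP neither allows nor forbids.

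Two further objections stand. Absence of DO is not always the best result, since filling may stop early for pain or fullness at a low volume. And not every woman is certain to have a baseline V1st: only the overreader reads it, and the documents do not say that eligibility waits for the overread.

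**Conclusion.** The concern holds in a limited form. The planned comparison of V1st selects on a post-randomisation outcome that treatment is meant to change, and the handling of 'not applicable' under LOCF is undefined. If the women are dropped, the damage is loss of the randomised comparison and a shrinking n in groups of six, with modest loss of the mean shift unless response is all-or-none. If baseline is carried, the effect is biased toward zero, slightly when few women lose DO and severely when many do. All sizes in mL depend on assumed thresholds, capacities and SDs.

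This should be fixed, but it does not threaten the trial. V1st is one of five analysed cystometric variables in an 18-woman safety study; SAP 7.3 calls efficacy exploratory with nominal P values, and dose escalation rests on safety review. The separate DO yes/no analysis captures abolition, though it does not make the V1st comparison valid.

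**What to change.** Before the blind is broken:

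1. In SAP 7.5 and 9.2, state that a 'not applicable' V1st is never filled by LOCF.
2. Label Table 14.2.4.4 descriptive, show the number without DO in each group at each visit, and cross-refer to Table 14.2.4.1.
3. Base the comparison at weeks 4 and 24 on all participants with a cystometry. Where no DO occurs, treat V1st as right-censored at the infused volume reached when filling stopped; if change from baseline is kept, censor it at that volume minus baseline V1st. Use a censored-data or exact rank method.
4. Use Cys Cap as the censoring value only where filling stopped at strong urge, because that is what it measures.
5. Rank 'no DO' as best only in a sensitivity analysis, since filling may stop early for pain or fullness.

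Cost: SAP wording and one revised table. The infused volume at the end of filling is not a named parameter in Table 2. It may be recoverable from the digitised recordings that Appendix D requires to be stored, but this needs checking. The result becomes a rank or censored comparison rather than a mean difference in mL, and it assumes that the end of filling is non-informative. That assumption is open to question, because treatment may also affect urge.
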